## **6.9 Packaging and Labeling**

The study drug ixazomib capsules will be provided by Millennium. The study drug will be labeled and handled as open-label material, and packaging labels will fulfill all requirements specified by governing regulations.

The capsules are individually packaged using cold-form foil-foil blisters that are in a child-resistant carton. There are 3 capsules in each wallet/carton.

## **6.10 Storage, Handling, and Accountability**

Upon receipt at the investigative site, ixazomib should remain in the blister and carton provided until use or until drug is dispensed. The container should be stored at the investigative site as per

labeled instructions (do not store above 30°C or 86°F, do not freeze). Ensure that the drug is used before the retest expiry date provided by Millennium. Expiry extensions will be communicated accordingly with updated documentation to support the extended shelf life.

In countries where local regulations permit, ixazomib capsules dispensed to the patient for take-home dosing should remain in the blister packaging and stored per labeled instructions as noted above until the point of use. The investigative site is responsible for providing the medication to the patient in the correct daily dose configurations. Comprehensive instructions should be provided to the patient in order to ensure compliance with dosing procedures. Patients who are receiving take-home medication should be given only 1 cycle of medication at a time. Patients should be instructed to store the medication per labeled instructions (not store above 30°C or 86°F, do not freeze) for the duration of each cycle. Patients should be instructed to return their empty blister packs to the investigative site, rather than discarding them. Reconciliation will occur accordingly when the patient returns for their next cycle of take-home medication. Any extreme in temperature should be reported as an excursion and should be dealt with on a case-by-case basis.

Ixazomib should be handled with due care. Patients should be instructed not to chew, break, or open capsules. In case of contact with broken capsules, raising dust should be avoided during the clean-up operation. The product may be harmful by inhalation, ingestion, or skin absorption. Gloves and protective clothing should be worn during cleanup and return of broken capsules and powder to minimize skin contact.

The area should be ventilated and the site washed with soap and water after material pick-up is complete. The material should be disposed of as hazardous medical waste in compliance with federal, state, and local regulations.

In case of contact with the powder (e.g., from a broken capsule), skin should be washed immediately with soap and copious amounts of water for at least 15 minutes. In case of contact with the eyes, copious amounts of water should be used to flush the eyes for at least 15 minutes. Medical personnel should be notified. Patients are to be instructed on proper storage, accountability, and administration of ixazomib, including that ixazomib is to be taken as intact capsules.

### **6.11 Study Compliance**

Study drug will be administered or dispensed only to eligible patients under the supervision of the investigator or identified sub-investigator(s). The appropriate study personnel will maintain records of study drug receipt and dispensing.

### **6.12 Treatment Assignment (*if applicable*)**

Open labeled single armed study, all subjects will receive study medications of ixazomib and rituximab dispensed from MD Anderson Institutional pharmacy.

### **6.13 Termination of Treatment and/or Study Participation**

Patients will be informed that they have the right to withdraw from the study at any time for any reason, without prejudice to their medical care. The investigator also has the right to withdraw patients from the study for any of the following reasons:

- Adverse event
- Protocol violation
- Lost to follow-up
- Progressive disease
- Study terminated

At the time of withdrawal, all study procedures outlined for the End of Study visit should be completed. The primary reason for patient's withdrawal from the study should be recorded in the source documents and CRF.

## **7. STATISTICAL AND QUANTITATIVE ANALYSES**

### **7.1 Statistical Methods**

**Primary endpoint:** complete response rate at 16 weeks measured using Lugano (2014)

#### **Patient populations**

All endpoints will be measured on patients that received at least one dose of the study drug.

### **7.1.1 Determination of Sample Size**

We plan to enroll 24 patients. When the true complete response rate at 4 months (week 16) is 30%, a cohort size of 24 subjects will provide a 95% confidence interval with a lower bound of 0.12 which is higher than the CR rate of 10% observed historically for Rituximab monotherapy.

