### **1.9 Study Rationale**

Therapy for Mantle cell lymphoma has evolved rapidly over the past decade. Ibrutinib, a Bruton's tyrosine kinase (BTK) inhibitor has set a new standard for relapsed MCL, with many ongoing studies for frontline utilization. However, patients who are refractory of ibrutinib face a difficult therapeutic challenge and poor survival outcome. One pathway believed to have significant role in ibrutinib refractoriness is over activation of the NFκB pathway. Proteasome inhibition has been a successful therapeutic intervention in relapsed MCL. However, the delivery logistics and side effects of proteasome inhibition have been difficult to manage and hence been underutilized. Therefore, ixazomib with its oral delivery system and milder side

effect profile would represent an improved modality for single and combination studies in this ibrutinib refractory MCL population.

Rituximab is a genetically engineered chimeric murine/human monoclonal antibody directed against the CD20 antigen expressed on the surface of normal and malignant B lymphocytes. Rituximab is approved by the US Food and Drug Administration (FDA) for the treatment of patients with low grade CD20+ B-cell NHL. Rituximab kills NHL cells by multiple mechanisms, including direct induction of apoptosis, and by stimulating antibody-dependent cellular cytotoxicity (ADCC) and complement-mediated cytotoxicity.

A retrospective analysis was performed to delineate the role of rituximab in the treatment of mantle cell lymphoma. Patients with newly-diagnosed MCL (n=37) and previously-treated MCL (n=50) received single-agent rituximab in the context of two multicenter clinical studies in 1996 and 1997. The overall response rate was 37% (30 of 81 evaluable patients). The complete response rate was 14%. There was no difference in response rates between newly-diagnosed and previously-treated patients. At a median follow-up of 1.4 years, the median time to disease progression was 7 months. The median duration of response was one year, and was significantly longer for patients achieving CR vs. PR (p=0.04).

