## **4. STUDY DESIGN**

### **4.1 Overview of Study Design**

Open label, single center, single –arm, phase II testing the combination of ixazomib and rituximab in the treatment of subjects with relapsed or refractory MCL. The study will enroll 24 patients. The treatment plan starts with oral ixazomib at the US approved dose of 4 mg. All subjects will have disease restaging at 8 weeks. Rituximab IV will be given once weekly for the first 4 weeks. Rituximab IV will restart at cycle 3, and continue monthly until cycle 12.

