### 7.1.6 Efficacy Analysis

Overall response and complete response at each of the pre-specified time points will be described as percentage with exact ninety-five percent (95%) confidence interval based on binomial distribution. PFS and OS curves will be described using Kaplan-Meier methods. The curves will be presented with 95% confidence intervals. Patients who are still on follow-up without experiencing the relevant event by the closeout date will be censored. The maximum grade of each toxicity will be described in tabular form as count and percentages.

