**7.1.9 Interim Analysis**

If early progression occurs in 2 or more of the first 5 patients, or 4 or more of the first 10 patients prior to the first restaging at week 16, the study will be closed for future enrollment. Using this rule, the probability of stopping the study early is 81.3% after 5 patients and 89.6% after 10 patients when the true rate of early progression is 50%. Early progression is defined as greater than 50% increase in the sum of bidirectional tumor measurement or new lesion prior to the first restaging at week 16.

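### The basis for N = 24 presents a lower confidence limit above 10% as assured when the true CR rate is 30%; with the planned exact interval and all 24 enrolled, its probability is 61%

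*Combined protocol and SAP*

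**What the plan says.** Section 7.1.1 gives the whole sample-size argument in two sentences. The first is "We plan to enroll 24 patients", which agrees with section 4.1 ("The study will enroll 24 patients"). The second sets a condition on the truth, "When the true complete response rate at 4 months (week 16) is 30" per cent, and concludes that "a cohort size of 24 subjects will provide a 95% confidence interval with a lower bound of 0.12". It then notes that this bound lies above a 10% CR rate attributed to earlier experience with rituximab alone. The section gives no power, no required number of CRs and no success rule.

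Other parts of the combined protocol and SAP bear on the point:

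- Section 7.1.6 specifies how the CR rate will be reported: a percentage with an "exact ninety-five percent (95%) confidence interval based on binomial distribution".
- Section 7.1, under Patient populations, sets the denominator: "All endpoints will be measured on patients that received at least one dose of the study drug".
- Section 7.1.9 has an early-progression rule, 2 or more of the first 5 patients or 4 or more of the first 10. If it is met "prior to the first restaging at week 16, the study will be closed for future enrollment".
- Section 1.9 describes a retrospective analysis of single-agent rituximab in mantle cell lymphoma: "The complete response rate was 14" per cent.

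**The concern.** The sentence moves from a true rate to a fixed confidence limit. With 24 patients and a true rate of 30%, the number of CRs varies from trial to trial, and the limit varies with it. Some of those counts give a lower limit below 10%. The sentence leaves this out and reads as though a true rate of 30% were enough to place the interval above the benchmark.

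The design has no control arm and no formal test, so comparison of this lower limit with the historical rate is the only argument offered for 24 patients. Someone relying on 7.1.1 to judge whether the trial is large enough would take a success probability near 1 from it. The wording could also mislead afterwards: 6 CRs in 24 would seem to contradict a true rate of 30%, although that count is quite likely at that rate.

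**Working it through.** **Inputs.** n = 24, assumed true CR rate 0.30, benchmark 0.10 and stated bound 0.12 (7.1.1); exact two-sided 95% binomial interval (7.1.6); all 24 patients dosed and counted (7.1).

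**1. Reproduce the 0.12.** The normal-approximation (Wald) limit at an observed rate of 0.30 is

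0.30 − 1.96 × √(0.30 × 0.70 / 24) = 0.1167, which rounds to 0.12.

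The figure is therefore correct for an observed 30%. That rate corresponds to 0.30 × 24 = 7.2 patients, which cannot occur, and the method is not the one planned in 7.1.6.

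**2. Limits under the planned method.** The exact (Clopper-Pearson) lower limit for x responders is the 2.5% quantile of a Beta(x, 24 − x + 1) distribution.

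| CRs of 24 | Observed rate | Exact 95% CI |
|---|---|---|
| 6 | 25.0% | 9.77% to 46.71% |
| 7 | 29.2% | 12.62% to 51.09% |
| 8 | 33.3% | 15.63% to 55.32% |

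At least 7 CRs are needed for a lower limit above 10%. The same count is needed for a limit of 0.12 or more.

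**3. Probability of at least 7 CRs.** With X binomial (24, p):

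| True CR rate p | P(X ≥ 7) |
|---|---|
| 0.30 | 0.6114 |
| 0.35 | 0.7894 |
| 0.40 | 0.9040 |

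At p = 0.30, P(X ≤ 6) = 1 − 0.6114 = 0.3886, and in all of those cases the lower limit is 9.8% or less. Exactly 6 CRs has probability 0.7712 − 0.6114 = 0.160.

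**4. Sensitivity to the interval method.** Wald limits also need 7 CRs (0.0768 at 6/24, 0.1098 at 7/24), so the probability is again 61.1%. Wilson or Jeffreys limits would need 6 (0.1200 and 0.1117 at 6/24), with probability 77.1%. With none of these methods is the result assured.

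**5. Early closure (7.1.9), not included above.** Let q be the probability of early progression, and A and B the numbers of early progressions in patients 1–5 and 6–10. Then

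P(stop by patient 10) = P(A ≥ 2) + P(A = 0) P(B ≥ 4) + P(A = 1) P(B ≥ 3).

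At q = 0.5 this is 0.8125 + (1/32)(6/32) + (5/32)(16/32) = 0.8965. The 0.8125 and 0.8965 match the plan's 81.3% and 89.6%. The documents give only q = 0.5; the other values of q are assumptions.

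| q | P(stop by patient 10) | P(no stop and ≥ 7 CRs), true CR 0.30 |
|---|---|---|
| 0.1 | 0.0845 | 0.5679 |
| 0.2 | 0.2886 | 0.4598 |
| 0.3 | 0.5357 | 0.3209 |
| 0.4 | 0.7521 | not computed |
| 0.5 | 0.8965 | not computed |

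The last column treats early progression and CR as mutually exclusive; a simulation of 400,000 trials agreed (0.568, 0.461, 0.321). It is the probability of enrolling all 24 and also seeing at least 7 CRs. It is not the probability that the limit exceeds 10%, because a trial that stops early still analyses everyone dosed.

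**6. Benchmark.** If the reference were the 14% of section 1.9, 7/24 (limit 12.6%) would not exceed it and 8/24 (15.6%) would. P(X ≥ 8) is 0.4353, 0.6425 and 0.8081 at true rates of 0.30, 0.35 and 0.40. The stated bound of 0.12 is itself below 14%.

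**The case against.** The best defence is that 7.1.1 describes precision in common shorthand. The plan names no hypothesis, power or success rule, and nothing is decided by whether the limit exceeds 10%; on this view, 61% is the power of a test the plan never set out. As a typical value 0.12 is fair, even slightly conservative: at a true rate of 30% the exact lower limit has median 0.126 and mean 0.136. Replacing the word for the true rate by one for the observed rate would largely repair the sentence.

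Part of this stands. The 0.12 is not a miscalculation, 61% contradicts no stated target, and the final interval will be the same however 7.1.1 is worded. But a precision statement would give the interval at an observed count. This one conditions on the truth and concludes that the bound lies above a benchmark, which is a claim about what the design will achieve.

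Two further objections limit the side points. First, the 7.1.9 rule is disclosed elsewhere in the protocol, and the joint figures fall mainly because fewer trials reach 24 patients. Among trials that do, the chance of at least 7 CRs is slightly higher than 61%: 0.5679/0.9155 = 62%, 0.4598/0.7114 = 65% and 0.3209/0.4643 = 69%. Early closure is therefore a caveat to the 61% and not evidence for the main point. Second, the 14% in section 1.9 pools newly diagnosed and previously treated patients, and 7.1.1 gives no source for its 10%. The documents do not settle which figure applies; the sponsor can be asked to reconcile them.

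**Conclusion.** The concern holds. The only argument for 24 patients states as certain a result that the design delivers about 6 times in 10 at its own assumed CR rate: 61.1%, with 38.9% of trials giving an exact lower limit of 9.8% or less. The fault lies in moving from a true rate to a limit that belongs to an observed one.

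The 61% rests on the exact interval of 7.1.6, the 10% benchmark, and 24 patients enrolled and counted. It makes no allowance for the early-progression rule in 7.1.9 or the neuropathy rule in 7.1.8, which may stop the current dose level. If patients without a week-16 assessment count as non-responders, the effective rate falls below 30% and so does the probability.

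The sentence should be corrected, but no planned analysis is invalidated. Confidence in the core figures is high; the results for early-progression rates other than 50% depend on assumption.

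**What to change.** First reconcile the 10% benchmark in 7.1.1 with the 14% CR rate in 1.9, and state the source of the one retained. If 10% stands, replace the second sentence of 7.1.1 with:

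> If 7 of 24 patients (29%) have CR, the exact 95% CI is 12.6% to 51.1%. The lower limit exceeds the 10% benchmark when at least 7 CRs are seen; if all 24 patients are enrolled, the probability of this is 61%, 79% and 90% for true CR rates of 30%, 35% and 40%. These figures do not account for the early-progression rule in 7.1.9.

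If 14% is adopted, the requirement becomes at least 8 CRs and the probabilities become 44%, 64% and 81%; the example interval should then be that for 8/24 (15.6% to 55.3%).

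Optionally, add the 7.1.9 stopping probabilities (8%, 29%, 54%, 75% and 90% at early-progression rates of 10% to 50%), marked as assumptions except at 50%.

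The cost is one reworded paragraph. N, the analysis and the decision rules do not change. The drawback is that the stated case for 24 patients becomes less favourable.

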- F. CT scans must include neck, chest, abdomen, pelvis and include oral and IV contrast. PET/CT performed at screening, at the end of Cycle 4, at the end of cycle 8, at the end of Cycle 15, and at the End of Study visit if not performed within the last 2 months. After Cycle 15, CT scans will be performed every 4 months. If PET/CT is performed and includes a CT scan of sufficient diagnostic quality and provides bidimensional nodal and liver and spleen measurements, an additional dedicated CT is not required at the time point. MRI may be used in place of CT at investigator's discretion.
- G. Bone marrow biopsies/aspirates at specified time points are mandatory (Screening, at the end of cycle 4, at the end of cycle 8, at the end of Cycle 15, and at the End of Study visit ) unless shown to be clear on previous examination by multi flow cytometry minimum sensitivity 10-4. \* If patient has progression on the study, we do require Bone marrow biopsy/aspiration at progression. For example, if week 9 imaging study shows clear progression beyond a reasonable doubt, we would like to perform a bone marrow biopsy/aspiration for end of study.
- H. Minimal residual disease assessment by ASO PCR in mantle cell lymphoma patients and flow cytometry. Peripheral blood will be collected from all patients as well as bone marrow aspirates in those patients required to undergo bone marrow aspirate and biopsy will be collected at Screening, at the end of cycle 4, at the end of cycle 8, at the end of cycle 15, and at the End of Study visit. Collect 20 mL's of blood in EDTA and 5 mL of a bone marrow aspirate in EDTA. Transport within 4 hours at room temperature to appropriate laboratory.

- I. Blood chemistry: Sodium, potassium, chloride, BUN, creatinine, glucose, calcium, total protein, albumin, AST, ALT, alkaline phosphatase, total bilirubin, LDH, phosphate, uric acid, magnesium and bicarbonate.

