11.4 Lugano Criteria 2014

Table 2. Revised Staging System for Primary Nodal Lymphomas		
Stage	Involvement	Extranodal (E) Status
Limited		
I	One node or a group of adjacent nodes	Single extranodal lesions without nodal involvement
II	Two or more nodal groups on the same side of the diaphragm	Stage I or II by nodal extent with limited contiguous extranodal involvement
II bulky*	II as above with “bulky” disease	Not applicable
Advanced		
III	Nodes on both sides of the diaphragm; nodes above the diaphragm with spleen involvement	Not applicable
IV	Additional noncontiguous extralymphatic involvement	Not applicable

NOTE. Extent of disease is determined by positron emission tomography-computed tomography for avid lymphomas and computed tomography for nonavid histologies. Tonsils, Waldeyer’s ring, and spleen are considered nodal tissue.
 
*Whether stage II bulky disease is treated as limited or advanced disease may be determined by histology and a number of prognostic factors.
		

Table 3. Revised Criteria for Response Assessment		
Response and Site	PET-CT–Based Response	CT-Based Response
Complete	Complete metabolic response	Complete radiologic response (all of the following)
Lymph nodes and extralymphatic sites	Score 1, 2, or 3* with or without a residual mass on 5PS† It is recognized that in Waldeyer’s ring or extranodal sites with high physiologic uptake or with activation within spleen or marrow (eg, with chemotherapy or myeloid colony-stimulating factors), uptake may be greater than normal mediastinum and/or liver. In this circumstance, complete metabolic response may be inferred if uptake at sites of initial involvement is no greater than surrounding normal tissue even if the tissue has high physiologic uptake	Target nodes/nodal masses must regress to $\leq 1.5$ cm in LDi No extralymphatic sites of disease
Nonmeasured lesion	Not applicable	Absent
Organ enlargement	Not applicable	Regress to normal
New lesions	None	None
Bone marrow	No evidence of FDG-avid disease in marrow	Normal by morphology; if indeterminate, IHC negative
Partial	Partial metabolic response	Partial remission (all of the following)

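### The 10% rituximab CR benchmark has no stated source or response criteria, and the plan does not say which Lugano 2014 definition of CR is to be compared with it

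*Combined protocol and SAP*

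**What the plan says.** Section 7.1.1 states that "We plan to enroll 24 patients". It assumes a true week-16 CR rate of 30%, derives from it a lower 95% limit of 0.12, and describes that limit as one "which is higher than the CR rate of 10% observed historically for Rituximab monotherapy". No reference, response criteria or imaging method is attached to the 10%.

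The only rituximab-alone results in the protocol are in Section 1.9. They come from a retrospective analysis of newly diagnosed (37) and previously treated (50) patients who "received single-agent rituximab in the context of two multicenter clinical studies in 1996 and 1997". It reports an overall response rate of 37% (30 of 81 evaluable) and a CR rate of 14%. How response was read is not stated.

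Section 7.1 sets the primary endpoint as CR at 16 weeks by Lugano 2014. The response table in Section 11.4 (Table 3) has a PET-CT column, in which CR is a score of 1, 2 or 3 "with or without a residual mass on 5PS", and a CT column, in which CR depends on node size. In Section 11.3 the imaging row of the schedule allows PET/CT or CT, while footnote F names PET/CT at screening and at the end of Cycle 4. Section 7.1.6 plans CR percentages with exact binomial 95% intervals and does not mention the two columns.

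**The concern.** There is no control arm, so the 10% is the only yardstick against which the CR rate is set. A historical rate is useful for this only if it counts the same event. Here the event may be counted by metabolic response, while the benchmark's definition is unknown. The only candidate source in the protocol predates the 2014 criteria by well over a decade and gives a different rate.

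At stake is the inference that the combination does better than rituximab alone. If the two rates rest on different definitions, a lower bound above 10% mixes any drug effect with a change in what is called CR, and the plan has no analysis that would separate them.

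**Working it through.** **1. The plan's own figure.** Inputs from Section 7.1.1: n = 24, CR rate 0.30. The normal-approximation lower bound is 0.30 − 1.96 × √(0.30 × 0.70 / 24) = 0.30 − 1.96 × 0.0935 = 0.1167, which rounds to 0.12. The figure is reproduced. The exact (Clopper-Pearson) method that Section 7.1.6 prescribes gives a similar value of 0.126 at 7/24, the attainable count nearest to 30%.

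**2. What the bound must exceed.** The number of CRs needed is the smallest count whose exact lower bound is above the benchmark. The power is P(X ≥ that count) for X ~ Binomial(24, 0.30).

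| CRs of 24 | Exact lower 95% bound |
|---|---|
| 6 | 0.0977 |
| 7 | 0.1262 |
| 8 | 0.1563 |

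- Against 10%, at least 7 CRs are needed; the chance at a true 30% is 0.611.
- Against the 14% of Section 1.9, at least 8 are needed; the chance at a true 30% is 0.435.
- The stated bound of 0.12 is above 10% but below 14%.

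If the 14% refers to the 81 evaluable patients, it is 11/81 = 13.6%, with exact 95% interval 7.0% to 23.0%. A true rate of 10% is compatible with those data, but 10% is not the rate they report.

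**3. The two definitions of CR in Table 3.**

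| Site | PET-CT column | CT column |
|---|---|---|
| Nodes and masses | Score 1 to 3, residual mass allowed | Target nodes 1.5 cm or less |
| Extralymphatic disease | Judged by the same score | None left |
| Marrow | No avid disease | Morphologically normal; immunohistochemistry if indeterminate |

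The columns can disagree in both directions. A node above 1.5 cm with score 2 can be CR by PET-CT but not by CT. A node of 1.5 cm or less with score 4 can be CR by CT but not by PET-CT. The marrow criteria can also disagree, and patients with marrow-only disease are eligible (Section 5.1).

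**4. Illustration of size.** Suppose ixazomib adds nothing, the rate under the benchmark's definition is 10%, and the trial's definition adds a net x to it. The documents give no value for x, so 0 to 15 points is an assumed range. The chance of an exact lower bound above 10% is P(X ≥ 7) for X ~ Binomial(24, 0.10 + x).

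| Assumed net x | CR rate | Chance that the lower bound exceeds 10% |
|---|---|---|
| 0 | 10% | 0.75% |
| 5 points | 15% | 5.7% |
| 10 points | 20% | 19% |
| 15 points | 25% | 39% |

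If the rituximab rate were simply 14%, with no shift of definition, the same chance would be 4.1%.

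**The case against.** The strongest reply is that a definitional bias is a possibility and not something the documents show. Most of this stands.

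- A reader might infer that the 10% comes from the 1996 and 1997 studies and was read by size. Section 1.9 reports 14% and gives no criteria, so neither step is supported. The benchmark's date and definition are simply unknown.
- A reader might infer that PET-CT is the wider definition and that the bias favours the trial. The columns are not nested, so x could be zero or negative. The populations also differ: the historical set includes newly diagnosed patients, while this trial requires at least two prior lines including a BTK inhibitor. The net direction is open.
- A reader might infer that PET/CT alone decides CR. Footnote F points that way, but the schedule row allows CT and both columns are appended.
- The 10% appears only in the sample-size argument. Section 7.1.6 sets no test or success threshold, so the chances in step 4 apply to a reading that Section 7.1.1 invites, not to a formal decision rule.
- The 39% requires the definition alone to move CR from 10% to 25%, and no figure in the documents supports that.

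What the reply does not remove is the gap itself. With no stated source, criteria or governing column, a reader of the results cannot tell whether the comparison is like for like. Differences in population are a further comparability problem; they do not cure this one.

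**Conclusion.** The point holds as a gap in specification. The benchmark is uncited, differs from the only rituximab-alone rate the protocol gives, and is set beside an endpoint with two possible definitions, neither of which is named as primary or matched to it. The firmest numerical consequence comes from the documents' own figures: moving the benchmark from 10% to 14% raises the requirement from 7 to 8 CRs of 24 and lowers the chance of meeting it at a true 30% from 61% to 44%.

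The effect of the definition is not quantified by the documents. The rise from 0.75% to 5.7%, 19% or 39% rests on an assumed net shift of 5, 10 or 15 points, a true 10% under the benchmark's definition and no ixazomib effect. It shows what is left uncontrolled and does not estimate a bias. It would be too strong to say that the definition explains an excess over 10%, or that it necessarily favours the trial.

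**What to change.** In Section 7.1.1, identify the source of the 10%, its response criteria and its imaging, and reconcile it with the 14% in Section 1.9. If 14% becomes the benchmark, restate the required number of CRs.

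In Section 7.1.6:

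- State which column of Table 3 gives the primary CR. PET-CT at the end of Cycle 4 fits footnote F.
- Also report week-16 CR by the CT column, with its exact 95% interval, from the same scans and the scheduled marrow. Under footnote F a separate dedicated CT is waived only if the PET/CT includes a CT of diagnostic quality and "provides bidimensional nodal and liver and spleen measurements", so the sizes are already secured. State how patients exempt from repeat marrow under footnote G are classified.
- Base any comparison with rituximab alone on the definition that matches the benchmark's source. If the source's criteria cannot be established, claim an improvement only if it holds under both definitions. CT-based CR is itself a 2014 definition, so it is like for like only if the source turns out to be size-based in the same way.

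The cost is plan wording and a second classification of data already collected, with no extra patients or scheduled scans. The downside is that the matched CR rate may be lower and that a both-definitions requirement is harder to meet.
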